#### **5.5.3.1 Dose Finding Using a Modified Toxicity Probability Interval Design**

The mTPI design [Ji Y, Li Y, Bekele BN 2007] of this study will target a DLT rate of 30%. The starting dose for the mTPI will be MK-7162 25 mg QD. Dose escalation and de-escalation decisions are based on the mTPI design and depend on the number of participants enrolled and number of DLTs observed at the current dose level.

A minimum of 3 participants are required at each dose. However, depending on the accrual rate and the occurrence of DLTs, 3, 4, 5, or 6 participants may be enrolled at each new dose level. In [Table 1], the columns indicate the numbers of participants treated at the current dose level, and the rows indicate the numbers of participants experiencing DLT. The entries of the table are the dose-finding decisions: E, S, D, and DU represent escalating the dose, staying at the same dose, de-escalating the dose, and excluding the dose from the trial due to unacceptable toxicity, respectively. For example, if 0 out of 3 participants at a given dose level develop a DLT, then the dose can escalate to the next level. If 2 participants out of 3 develop a DLT, the dose will be de-escalated to the next lower dose level. If 3 out of 3 participants develop a DLT, this indicates an unacceptable toxicity at this dose. The dose should be de-escalated and the current dose will not be explored further. If 1 out of 3 participants at a given dose level develops a DLT, then additional participants should be enrolled at that dose level following the rules below.

When adding participants to a dose level in response to a “stay” decision, the same principles will be applied whether 3, 4, 5, or 6 participants are initially enrolled at that dose level. First, the number of additional participants to be enrolled is capped to minimize the exposure to a dose that may be unacceptably toxic (denoted as DU in [Table 1]). Secondly, to determine how many more participants can be enrolled at the dose level, one can count steps in diagonal direction (down and to the right) from the current cell to the first cell marked DU. For example, if 1 of 3 participants have experienced a DLT at a given dose level, no more than an additional 3 participants should be enrolled at this dose level until additional DLT data are available. This is because this dose level would be considered unacceptably toxic if all 3 of the additional participants experience a DLT (ie, 4/6 participants with DLT in [Table 1]).

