
A D or DU decision at the lowest dose level will stop the trial. An E decision at the highest dose level will result in staying at that level. During dose finding, it may be acceptable to de-escalate to an intermediate dose that was not predefined and not previously studied if evaluation of toxicity at such a dose is desired. If this approach is taken, 3 to 6 new participants may be enrolled at the new intermediate dose, and the aforementioned rules should be used to determine further enrollment at this dose level.

Dose finding will end after 14 participants have been enrolled at any of the tested doses (including intermediate doses). In the event the dose-finding decision is not to stay at the current dose based on the 14 participants, the dose may be escalated or de-escalated and additional participants may be treated.

The pool-adjacent-violators-algorithm [Ji, Y. and Wang, S.-J. 2013] will be used to estimate the DLT rates across doses. The dose with an estimated DLT rate closest to 30% will be treated as a preliminary MTD. The final RP2D for future studies will be based on all available safety and tolerability assessments from the Dose Escalation and Confirmation Phase, Dose Expansion Phase, as well as PK and PD data, and preliminary efficacy assessments from this trial.

Note that although 30% was the target toxicity rate used to generate the guidelines in [\[Table 1\]](#), the observed rates of participants with DLTs at the MTD may be slightly above or below 30%.

Table 1 Dose-finding Rules per mTPI Design

Number of participants with at least 1 DLT	Number of Participants Evaluable for DLT at Current Dose											
	3	4	5	6	7	8	9	10	11	12	13	14
0	E	E	E	E	E	E	E	E	E	E	E	E
1	S	S	S	E	E	E	E	E	E	E	E	E
2	D	S	S	S	S	S	S	E	E	E	E	E
3	DU	DU	D	S	S	S	S	S	S	S	S	S
4		DU	DU	DU	D	D	S	S	S	S	S	S
5			DU	DU	DU	DU	DU	D	S	S	S	S
6				DU	DU	DU	DU	DU	D	S	S	S
7					DU	D						
8						DU						
9							DU	DU	DU	DU	DU	DU
10								DU	DU	DU	DU	DU
11									DU	DU	DU	DU
12										DU	DU	DU
13											DU	DU
14												DU

DLT = Dose limiting toxicity; D = De-escalate to the next lower dose; DU = The current dose is unacceptably toxic; E = Escalate to the next higher dose; S = Stay at the current dose.

Target toxicity rate = 30%

Flat noninformative prior Beta (1,1) is used as a prior and  $\epsilon_1=\epsilon_2=0.03$  [Ji Y, Li Y, Bekele BN 2007], [Ji, Y., et al 2007], [Ji, Y. and Wang, S.-J. 2013]

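### Does the mTPI decision table (Table 1) contradict the parameters in its own footnote at 2/10, 6/11 and 6/12?

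*Combined protocol and SAP*

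**What the plan says.** Section 5.5.3.1 bases each escalation decision on the number evaluable and the number with a DLT at the current dose, and reads the decision from Table 1. It states that "30% was the target toxicity rate used to generate the guidelines in" that table. The footnote adds "Flat noninformative prior Beta (1,1) is used as a prior and" epsilon1 = epsilon2 = 0.03.

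In the text of the PDF, the row for 2 DLTs (n = 3 to 14) reads "2 D S S S S S S E E E E E", so 2/10 is E. The row for 5 DLTs (n = 5 to 14) reads "5 DU DU DU DU DU D S S S S", so 5/9 is DU. The row for 6 DLTs (n = 6 to 14) reads "6 DU DU DU DU DU D S S S", so 6/11 is D and 6/12 is S.

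DU is described only in words, as unacceptable toxicity. Neither Section 5.5.3.1 nor Section 10 gives a probability cut-off. The DU cells also cap enrolment after a stay decision: one is to "count steps in diagonal direction (down and to the right) from the current cell to the first cell marked DU".

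**The concern.** Table 1 is the operating rule for the primary objective, and a reader should be able to regenerate it from the stated inputs. Taken at face value, three things fail.

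- 2/10 escalates where the footnote parameters stay.
- 6/12 stays where they de-escalate. It also sits oddly beside 4/8 and 5/10, which are D at the same observed rate of 50% with fewer participants.
- 5/9 is DU while 6/11, with stronger evidence of a rate above 30%, is only D. No single cut-off allows both.

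All three entries would be more permissive than the stated rule (6/11 on the assumed 0.95 cut-off). The enrolment cap would move too. From 4/9 the diagonal runs 5/10, 6/11, so the cap is 2 if 6/11 is DU and at least 3 if it is D. In a simulation with assumed DLT curves, a trial acted on one of these cells in 0.1 to 8.3% of runs with a first cohort of 3, 5 or 6 and additions of 3. The figure was 9.3 to 24.1% when cohort sizes landed on n = 10.

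**Working it through.** **Inputs.** From the Table 1 footnote: target 0.30, prior Beta(1,1), epsilons 0.03, giving the intervals E (0, 0.27), S (0.27, 0.33) and D (0.33, 1). Assumed, because the documents cite the method without printing its formulas: the decision is the interval with the largest unit probability mass (UPM), and a dose is DU if P(p > 0.30) exceeds a cut-off.

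**Formula.** With x DLTs in n, the posterior is Beta(1+x, 1+n−x), and UPM = posterior probability of the interval ÷ its length.

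**The plan's own figures first.** With a cut-off of 0.95, 75 of the 78 cells in rows 0 to 6 come out as printed (12+12+12+12+11+10+9 = 78). The formulas are therefore the right ones. The exceptions are:

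| Cell | UPM E | UPM S | UPM D | P(p > 0.30) | Rule | Text |
|---|---|---|---|---|---|---|
| 2/10 | 0.6049/0.27 = 2.24 | 0.1537/0.06 = 2.56 | 0.2413/0.67 = 0.36 | 0.313 | S | E |
| 6/11 | 0.08 | 0.69 | 1.40 | 0.961 | DU | D |
| 6/12 | 0.0365/0.27 = 0.14 | 0.0623/0.06 = 1.04 | 0.9012/0.67 = 1.35 | 0.938 | D | S |

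For comparison, P(p > 0.30) is 0.942 at 4/7 (D), 0.953 at 5/9 (DU), 0.901 at 4/8 (D) and 0.922 at 5/10 (D). As read, the mismatch is real.

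**Could other parameters have produced the table?** A grid of 3,825 combinations of the two epsilons and the cut-off never gave fewer than 3 mismatches. Of 1,600 epsilon pairs, none gives 6/12 = S together with D at 4/8 and 5/10. A misprinted footnote does not explain the cells.

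**Could a slip in the text explain them?** Under the footnote, E in row 2 begins at 2/11 (UPM E 2.48, S 2.40). In row 6, D falls at 6/12 and S begins at 6/13 (UPM S 1.45, D 1.28). Each change comes one column to the right of where the text has it:

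- Row 2: the text has D, six S, five E. The rule gives D, seven S, four E. Both have 12 entries.
- Row 6: the text has five DU, D, three S. The rule gives six DU, D, two S. Both have 9 entries.

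With those two rows moved by one column, 78 of 78 cells match at cut-offs of 0.943, 0.945, 0.95 and 0.952. The 5/9 against 6/11 conflict disappears, because both are then DU.

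**Is the text known to be damaged in this way?** Yes. Row 7 reads only DU, D, which would put D at 7/8 beside DU at 6/8, an impossible ordering. Row 8 is a single DU. At 0.95 the rule gives row 7 as DU for n = 7 to 13 and D at n = 14 (P = 0.949987), and row 8 as DU throughout. With the repeats removed, these are exactly the fragments in the text. Neither row was used in the 78-cell count.

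**The case for a change.** The best argument for the concern is that rows 2, 5 and 6 carry full entry counts (12, 10 and 9), so a simply dropped cell cannot explain them. Row 2 would have to lose an S and gain an E, and row 6 lose a DU and gain an S. The worked examples in Section 5.5.3.1 (0/3, 1/3, 2/3, 3/3 and 4/6) also agree with the cells as read.

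The point about counts stands as far as it goes, but a one-column shift preserves the count. The examples do not reach the cells in question: 2/3 lies left of the shifted part of row 2, and none is in row 6. It also remains true that a typing slip by the authors would look the same in this text, and only the page image can separate the two. But a discrepancy confined to two rows of a table that is demonstrably corrupted elsewhere is no evidence of an error in the plan.

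The missing DU cut-off does not depend on any of this, and that part is correct. It limits a reader's ability to regenerate the table. It does not affect conduct, because decisions and enrolment caps are taken from the finished cells.

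**Conclusion.** The concern does not hold as an error in the plan. The arithmetic at the cells as read is right, but the three mismatches reduce to two one-column slips, in rows 2 and 6. Correcting those slips gives complete agreement with the footnote (78 of 78), while every alternative parameter setting tried leaves at least three cells wrong. This rests on the usual mTPI formulas and on a DU cut-off between about 0.943 and 0.952, neither of which is printed. The formulas are supported by the 75 cells that match without any adjustment, and a cut-off of 0.95 by the remnants of rows 7 and 8.

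The simulated frequencies count visits to the cells, not changes in the dose selected. Under Section 5.5.3.1 the preliminary MTD comes from pool-adjacent-violators estimates, and Section 5.1.1 weighs the totality of data before a dose is carried forward. The unstated DU cut-off is a minor gap in reporting.

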## 6. Study Population

Male and female participants at least 18 years of age with advanced solid tumors (of any type) will be enrolled in this trial.

Prospective approval of protocol deviations to recruitment and enrollment criteria, also known as protocol waivers or exemptions, is not permitted.

## 6.1 Inclusion Criteria

Participants are eligible to be included in the study only if all of the following criteria apply:

1. Have a histologically- or cytologically-confirmed advanced/metastatic solid tumor by pathology report and have received, or been intolerant to, or been ineligible for all treatment known to confer clinical benefit. Participants with solid tumors of any type are eligible for enrollment.
2. Have stage III or stage IV disease that is not surgically resectable.
3. Have measurable disease by RECIST 1.1 criteria as assessed by the local site investigator/radiology. Lesions situated in a previously irradiated area are considered measurable if progression has been demonstrated in such lesions.
4. Be  $\geq 18$  years of age on the day of signing informed consent.
5. Have one or more discrete malignant lesions that are amenable to a minimum of two separate biopsies guided by one of the following modalities: visual inspection, ultrasound guidance, or cross-sectional image guidance (computed tomography/magnetic resonance imaging [CT/MRI]).

Note: Participants should only be enrolled if during the screening assessment the investigator deems the biopsy of such lesions to be medically safe.

6. Have an evaluable baseline tumor sample to submit for analysis. Archival samples are preferred, if available. Details pertaining to tumor tissue submission can be found in the Procedures Manual.
7. Have a performance status of 0 or 1 on the Eastern Cooperative Oncology Group (ECOG) Performance Scale.
8. Demonstrate adequate organ function as defined by the following table ([[Table 2](#)])

All screening evaluations should be performed within the Screening period, and labs are to be obtained within 7 days of initiation of treatment.

Table 2 Adequate Organ Function Laboratory Values

System	Laboratory Value
Hematological	
Absolute neutrophil count	$\geq 1,500/\text{mcL}$
Platelets	$\geq 100,000/\text{mcL}$
Hemoglobin	$\geq 9 \text{ g/dL}$ or $\geq 5.6 \text{ mmol/L}$ a
Renal	
Serum creatinine or creatinine clearance (CrCl) (measured or calculated) b or Glomerular Filtration Rate (GFR) in place of CrCl	$\leq 1.5 \times \text{upper limit of normal (ULN)}$ or $\geq 60 \text{ mL/min}$ for participant with creatinine levels $\geq 1.5 \times \text{ULN}$
Hepatic	
Total bilirubin (serum)	$\leq 1.5 \times \text{ULN}$ or Direct bilirubin $< \text{ULN}$ for participants with total bilirubin levels $\geq 1.5 \times \text{ULN}$
Aspartate aminotransferase (AST) and Alanine aminotransferase (ALT)	$< 2.5 \times \text{ULN}$ or $\leq 5 \times \text{ULN}$ for participants with liver metastases
Coagulation	
International Normalized Ratio (INR) or Prothrombin Time (PT)	$< 1.5 \times \text{ULN}$ unless participant is receiving anticoagulant therapy
Activated Partial Thromboplastin Time (aPTT) or Partial Thromboplastin Time (PTT)	$< 1.5 \times \text{ULN}$ unless participant is receiving anticoagulant therapy

a Criteria must be met without packed red blood cell (pRBC) transfusion within the prior 2 weeks. Participants may be on stable doses of erythropoietin (<math>\geq</math> approximately 3 months).
 
b Creatinine clearance (CrCl) should be calculated per institutional standard.
 
Note: This table includes eligibility-defining laboratory value requirements for treatment; laboratory value requirements should be adapted according to local regulations and guidelines for the administration of specific chemotherapies.
	

## Demographics

Male participants:

9. A male participant must agree to use a contraception, and refrain from donating sperm, as detailed in Appendix 5 of this protocol during the treatment period and for at least 120 days, corresponding to time needed to eliminate any study treatments (MK-7162 and pembrolizumab), after the last dose of study treatment.

Female participants:

10. A female participant is eligible to participate if she is not pregnant (Appendix 5), not breastfeeding, and at least one of the following conditions applies: A woman of childbearing potential (WOCBP) who agrees to follow the contraception guidance in Appendix 5 during the treatment period for at least 120 days (corresponding to time needed to eliminate any study treatment(s) (MK-7162 and pembrolizumab).

### **Informed Consent**

11. The participant (or legally acceptable representative if applicable) provides written informed consent. The participant may also provide consent for future biological research (FBR). However, the participant may consent to the main trial without participating in FBR.

### **6.2 Exclusion Criteria**

Participants are excluded from the study if any of the following criteria apply:

#### **Medical Conditions**

1. Has a history of a second malignancy, unless potentially curative treatment has been completed with no evidence of malignancy for 2 years.

Note: The time requirement does not apply to participants who underwent successful definitive resection of basal cell carcinoma of the skin, superficial bladder cancer, *in situ* cervical cancer, or other *in-situ* cancers.

2. Has a known active central nervous system (CNS) metastasis and/or carcinomatous meningitis. Participants with previously treated brain metastases may participate provided they are radiologically stable, ie, without evidence of progression for at least 4 weeks by repeat imaging (note that this repeat imaging should be performed during study screening), clinically stable and without requirement for steroid treatment for at least 14 days prior to first dose of study treatment.
3. Has had a severe hypersensitivity reaction to treatment with a monoclonal antibody/components of the study drug(s).
4. Has an active autoimmune disease that has required systemic treatment in the past 2 years (ie, with use of disease-modifying agents, corticosteroids, or immunosuppressive drugs) except vitiligo or resolved childhood asthma/atopy. Replacement therapy, such as thyroxine, insulin, or physiologic corticosteroid replacement therapy for adrenal or pituitary insufficiency, is not considered a form of systemic treatment and is allowed. Use of non-systemic steroids is permitted.
5. Has a history of vasculitis.
6. Has an active infection requiring systemic therapy.
7. Has symptomatic ascites or pleural effusion. A participant who is clinically stable following treatment for these conditions (including therapeutic thoracentesis or paracentesis) is eligible.

8. Has interstitial lung disease that has required oral or intravenous glucocorticoids to assist with management.
9. Has a history of (non-infectious) pneumonitis that required steroids or has current pneumonitis.
10. Has undergone prior allogeneic hematopoietic stem cell transplantation within the last 5 years.

Note: Participants who have had a stem cell transplant greater than 5 years ago are eligible as long as there are no symptoms of graft-versus-host disease (GVHD).

11. Has a known history of human immunodeficiency virus (HIV) infection. No HIV testing is required unless mandated by local health authority.

12. Has known active Hepatitis B (defined as Hepatitis B surface antigen [HBsAg] reactive) or known active Hepatitis C virus (defined as HCV RNA [qualitative] is detected) infection.

Note: No testing for Hepatitis B and Hepatitis C is required unless mandated by local health authority.

13. Has a history or current evidence of any condition, therapy, or laboratory abnormality that might confound the results of the study, interfere with the participant's participation for the full duration of the study, make administration of the study drugs hazardous, or make it difficult to monitor adverse effects such that it is not in the best interest of the participant to participate, in the opinion of the treating investigator.

14. Has known psychiatric or substance abuse disorders that would interfere with the participant's ability to cooperate with the requirements of the study.

15. Is pregnant or breastfeeding, or expecting to conceive or father children within the projected duration of the study.

16. Has not fully recovered from any effects of major surgery without significant detectable infection. Surgeries that required general anesthesia must have been completed at least 2 weeks before first study drug administration. Surgery that required regional/epidural anesthesia must have been completed at least 72 hours before first study drug administration and participants should have recovered.

17. A WOCBP who has a positive urine pregnancy test within 72 hours prior to treatment allocation (see Appendix 5). If the urine test is positive or cannot be confirmed as negative, a serum pregnancy test will be required.

Note: In the event that 72 hours has elapsed between the screening pregnancy test (urine or serum) and the first dose of study treatment, repeat pregnancy testing must be performed and must be negative in order for participant to start receiving study medication.

### Prior/Concomitant Therapy

18. Has received prior systemic anti-cancer therapy including investigational agents or has used an investigational device within 28 days prior to the first dose of study treatment.

Note: Participants must have recovered from all AEs due to previous therapies to  $\leq$  Grade 1 or baseline. Participants with  $\leq$  Grade 2 neuropathy or alopecia may be eligible. Participants receiving ongoing replacement hormone therapy for endocrine immune-related adverse events will not be excluded from participation in this study.

Note: Prior exposure to immunotherapeutics is allowed, including PD-1 and PD-L1 inhibitors, provided the participant did not experience  $\geq$  Grade 3 drug-related toxicity on monotherapy with a PD-1 or PD-L1 inhibitor.

19. Has been previously treated with an IDO1 inhibitor (eg, epacadostat, BMS-986205)

20. Has received prior radiotherapy within 2 weeks of start of study treatment.

Participants must have recovered from all radiation-related toxicities, not require corticosteroids, and not have had radiation pneumonitis. A 1-week washout is permitted for palliative radiation ( $\leq$  2 weeks of radiotherapy) to non-CNS disease.

21. Is receiving an MAO-inhibitors (MAOI) or any drug which has significant MAOI activity (eg, meperidine, linezolid, methylene blue) within the 21 days before screening, or has a history of Serotonin Syndrome after receiving serotonergic drugs.

22. Is expected to require any non-protocol antineoplastic therapy while on study.

23. Has a diagnosis of immunodeficiency or is receiving chronic systemic steroid therapy in excess of replacement doses (the equivalent of prednisone  $\leq$  10 mg/day is acceptable), or on any other form of immunosuppressive medication.

Note: The use of physiologic replacement doses of corticosteroids may be approved after consultation with the Sponsor Medical Monitor or designee.

24. Has received a live-virus vaccine within 30 days prior to first dose of study medication. Vaccines that do not contain live virus are permitted.

### 6.3 Lifestyle Restrictions

#### 6.3.1 Dietary Restrictions

For C1D1, C1D15 and C3D1 participants are to remain fasted overnight. The participant must remain fasting up to 1 hour following treatment with MK-7162 on C1D1, C1D15, and C3D1; clear fluids are permitted.

There are no other diet restrictions.

#### 6.3.2 Contraception

MK-7162 and pembrolizumab may have adverse effects on a fetus in utero. Furthermore, it is not known if MK-7162 or pembrolizumab have transient adverse effects on the composition of sperm.

For this study, male participants will be considered to be of non-reproductive potential if they have azoospermia (whether due to having had a vasectomy or due to an underlying medical condition).

### **6.3.3 Pregnancy**

If a participant inadvertently becomes pregnant while on treatment with MK-7162 and/or pembrolizumab, the participant will be immediately discontinued from study treatment. The site will contact the participant at least monthly and document the participant's status until the pregnancy has been completed or terminated. The outcome of the pregnancy will be reported to the Sponsor without delay and within 24 hours if the outcome is a serious adverse experience (eg, death, abortion, congenital anomaly, or other disabling or life-threatening complication to the mother or newborn). The study Investigator will make every effort to obtain permission to follow the outcome of the pregnancy and report the condition of the fetus or newborn to the Sponsor. If a male participant impregnates his female partner, the study personnel at the site must be informed immediately and the pregnancy must be reported to the Sponsor and followed as described in Section 9.3.6.

